1. STUDY OBJECTIVES

1.1. SPECIFIC AIM 1

- To investigate the safety of in-hospital thromboprophylaxis with twice-daily low-dose enoxaparin thromboprophylaxis (starting dose, 0.5 m/gkg subcutaneously q12 hours, adjusted to achieve a 4 hour post-dose anti-factor Xa level of 0.20-0.49 anti-Xa U/mL) in children hospitalized with COVID-19 related-illnesses, as measured by the cumulative incidence of ISTH-defined [10] clinically-relevant bleeding (primary endpoint).

1.2. SPECIFIC AIM 2

- To determine the median twice-daily enoxaparin dose, as measured in mg/kg, required to achieve a 4 hour post-dose anti-factor Xa level of 0.20-0.49 anti-Xa U/mL in children hospitalized with COVID-19 related-illnesses, and to compare dose-requirements by age group (birth to <1 year old, 1-<6 years old, 6-<13 years old, and 13-<18 years old).

1.3. SPECIFIC AIM 3

- To investigate, on an exploratory basis, the efficacy of in-hospital thromboprophylaxis with twicedaily enoxaparin in children hospitalized with COVID-19, as measured by the proportion of serial D-dimer levels obtained at standardized time points that are <2 times the upper limit of normal (<2x ULN) values for age (Aim 3a; surrogate marker of efficacy), the cumulative incidence of radiologically-confirmed HA-VTE (Aim 3b; clinical efficacy), and the median duration of in-hospital increased respiratory support (new requirement for high-flow nasal cannula, non-invasive ventilation, and/or mechanical ventilation, relative to any at-home baseline requirement; Aims 3c, clinical efficacy).

2. STUDY DESIGN

The study is a phase 2, single-arm, open-label, non-randomized clinical trial conducted at 12 centers in the US to evaluate the safety, dose-requirements, and exploratory efficacy of twice-daily subcutaneous enoxaparin as in-hospital venous thromboembolism (VTE) prophylaxis in children (birth to 18 years) hospitalized with signs and/or symptoms of SARS-CoV-2 infection (i.e., COVID-19) including COVID-19 multisystem inflammatory syndrome (MISC)

2.2. TREATMENT GROUPS One

2.3. STUDY POPULATION

Inclusion Criteria

- 1. Children (birth to <18 years of age)
- 2. Positive nucleic acid test, antigen testing, or antibody testing for SARS-CoV-2 within the past 7 days
- 3. Hospitalized <72 hours post-admission
- 4. One or more signs and/or symptoms of COVID-19 illness within the past 72 hours, as follows:

i.) Cough

- ii.) Fever (oral temperature >100.4°F/38°C)
- iii.) Chest pain
- iv.) Shortness of breath
- v.) Myalgia
- vi.) Acute unexplained loss of smell or taste
- vii.) New/increased supplemental oxygen requirement
- viii.) Acute respiratory failure requiring non-invasive or invasive ventilation
- ix.) Encephalitis

5. Clinical suspicion that the above symptoms are related to COVID-19 infection and not an alternative etiology.

Inclusion Criteria for MIS-C Patients Who Do Not Already Meet the Above Criteria for COVID-Infected Patients:

- 1. 1. Children (birth to <18 years of age)
- 2. 2. Signs and symptoms of COVID-19 Multi-System Inflammatory Syndrome (MIS-C) including: i.) fever ≥ 3 days;
- 3. ii.) Two or more of the following: a) Rash of bilateral non-purulent conjunctivitis or mucocutaneous inflammation (oral, hands, or feet),
- 4. b) Hypotension or shock,
- 5. c) Features of myocardial dysfunction, pericarditis, valvulitis, or coronary abnormalities (including ECHO findings or elevated troponin/NT-proBNP),
- 6. d) Evidence of coagulopathy (by PT, PTT, or d-Dimer)
- 7. e) Acute gastrointestinal problems (diarrhea, vomiting, abdominal pain)
- 8.
- 9. iii.) Elevated markers of inflammation (erythrocyte sedimentation rate, C-reactive protein, or pro-calcitonin);
- 10. iv.) No other obvious microbial cause of inflammation, including bacterial sepsis, staphylococcal or streptococcal shock syndrome;
- 11. v.) Known exposure to a SARS-CoV-2 positive case, as documented by clinical history

Exclusion Criteria

1) Patient's expected length of hospitalization is < 2 days

2) Receiving therapeutic dosing of anticoagulation (NOTE: pre-enrollment prophylactic enoxaparin administration is not an exclusion criterion)

3) Receiving ASA dosing > 5 mg/kg/day

4) Clinical-relevant bleeding (see criteria under Primary Outcome, below) within the past 72 hours

5) Platelet count <50,000/ μ L within the past 24 hours

6) Prothrombin time (PT) ≥2 seconds above the upper limit of age-appropriate local reference range within the past 24 hours

7) Activated partial thromboplastin time (aPTT) ≥4 seconds above the upper limit of ageappropriate local reference range within the past 24 hours

8) Fibrinogen level <75 mg/dL

9) Severe renal impairment, as defined by estimated glomerular filtration rate (eGFR) <31 mL/min/1.73 m2, as calculated by the Schwartz formula

10)Parent or legally authorized representative unwilling to provide informed consent for patient participation.

2.4. EXPOSURE

Enoxaparin dose

2.5. SAMPLE SIZE

The study enrolled 38 participants

3. OUTCOME VARIABLES

3.1. PRIMARY OUTCOME(S)

Safety: Occurrence of clinically-relevant (i.e., major plus clinically relevant non-major [CRNM]) bleeding within 30 days.

3.2. SECONDARY OUTCOMES

Median twice-daily enoxaparin dose, as measured in mg/kg, required to achieve a 4 hour post-dose anti-factor Xa level of 0.20-0.49 anti-Xa U/mL.

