# B. **Principal Aims and Hypotheses**

**Specific Aim 1:** To investigate the safety of in-hospital thromboprophylaxis with twicedaily low-dose enoxaparin thromboprophylaxis (starting dose, 0.5 m/gkg subcutaneously q12 hours, adjusted to achieve a 4 hour post-dose anti-factor Xa level of 0.20-0.49 anti-Xa U/mL) in children hospitalized with COVID-19 related-illnesses, as measured by the cumulative incidence of ISTH-defined [10] clinically-relevant bleeding (primary endpoint).

Hypothesis 1: The observed cumulative incidence of ISTH-defined clinicallyrelevant bleeding is ≤2.6% (upper limit of 90% confidence interval: ≤11.8%) among children with COVID-19 who receive in-hospital thromboprophylaxis with twicedaily low-dose enoxaparin.

**Specific Aim 2:** To determine the median twice-daily enoxaparin dose, as measured in mg/kg, required to achieve a 4 hour post-dose anti-factor Xa level of 0.20-0.49 anti-Xa U/mL in children hospitalized with COVID-19 related-illnesses, and to compare dose-requirements by age group (birth to <1 year old, 1-<6 years old, 6-<13 years old, and 13-<18 years old).

Hypothesis 2: Median dose-requirement for anti-Xa-targeted thromboprophylaxis with twice-daily enoxaparin, as measured in mg/kg, in children hospitalized with COVID-19 are associated with age, with younger age groups requiring higher doses.

**Specific Aim 3 (Exploratory):** To investigate, on an exploratory basis, the efficacy of inhospital thromboprophylaxis with twice-daily enoxaparin in children hospitalized with COVID-19, as measured by the proportion of serial D-dimer levels obtained at standardized time points that are <2 times the upper limit of normal (<2x ULN) values for age (Aim 3a; surrogate marker of efficacy), the cumulative incidence of radiologicallyconfirmed HA-VTE (Aim 3b; clinical efficacy), and the median duration of in-hospital increased respiratory support (new requirement for high-flow nasal cannula, non-invasive ventilation, and/or mechanical ventilation, relative to any at-home baseline requirement; Aims 3c, clinical efficacy).

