# D. Summary of Research Methods and Study Design

The study design is a phase 2, single-arm, open-label, non-randomized clinical trial conducted among the Kids-DOTT Investigators Group, at 12-15 of the Kids-DOTT participating centers. The list of participating Kids-DOTT centers (including primary and alternate/supplemental sites) is shown in Appendix 1. Study activity at each site will be

overseen by either a pediatric hematologist, pediatric intensivist, or pediatric hospitalist as the site principal investigator, in close collaboration with sub-investigators from the other two aforementioned specialties.

The Clinical Coordinating Center (CCC) and Data Coordinating Center (DCC) for this nonblinded, non-randomized phase 2 trial are at Johns Hopkins All Children's Hospital (JHACH; St. Petersburg, FL), led by Johns Hopkins University School of Medicine faculty based on that campus (Appendix 2. CCC). Coordinating center personnel have extensive experience in the conduct of numerous large collaborative clinical trials, with specific expertise in pediatric phase 1-3 trials. CCC and DCC key personnel include:

Overall (National) Principal Investigator: Steering Committee Chair: Clinical Endpoint Adjudication Ctte Chair: Data and Safety Monitoring Board Chair: Medical Safety Officer: Multi-Site Project Managers:

Lead Biostatistician: Biorepository Manager: [name], MSc [name], PhD [name] [name], MPH [name], PhD [name], MS (CCC) [name], MBA-IT (DCC) [name] [name], MS, MT

Anticoagulant (low-dose enoxaparin) thromboprophylaxis dosing regimen is as follows for inpatient use only:

- Enoxaparin starting dose 0.5 mg/kg (max starting dose: 60 mg) subcutaneously q12 hours, adjusted to achieve a 4 hour post-dose anti-factor Xa level of 0.20-0.49 anti-Xa U/mL after the 1st or 2nd dose.
  - For anti-Xa values <0.20 U/mL, the enoxaparin dose will be increased by 10-20%, and a 4 hour post-dose anti-Xa level will be obtained after the 1st or 2nd dose at the new dosing regimen.
  - For anti-Xa values ≥0.5 U/mL, the enoxaparin dose will be decreased by 10-20%, and a 4 hour post-dose anti-Xa level will be obtained after the 1st or 2nd dose at the new dosing regimen.

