# E. Description of Population to be Enrolled

#### 1. Target Enrollment

The target accrual is based on the primary endpoint (safety). The safety population is defined as all patients who received at least one dose of the enoxaparin regimen. In order to achieve adequate power and precision for determination of safety in the primary analysis (see also section G, below), the target enrollment is 38 evaluable children, from among a total of 12-15 participating sites. Participants who do not received at least one dose of the enoxaparin regimen (i.e. early termination, withdrawal of consent) will be replaced. Anticipating an 85% retention rate, we will enroll up to 45 participants. Both males and females of all races and ethnic groups are eligible for this study.

Table 1. Schedule of Assessments.

Assessment	Screening (Within 72 hours of hospital admission)	Enrollm ent Day 0	Day 1	Day 2	Day 3 *	Day 7 *	Day 14 *	Day 30 (+/- 2 days)
Informed consent		Х						
Enrollment		Х						
Full H&P	Х							
Focused H&P			Х	Х	Х	Х	Х	
Weight	Х							
CBC with platelet count	Х				Х	Х	Х	
PT and aPTT 	Х				Х	Х	Х	
Fibrinogen 	Х				Х	Х	Х	
Serum creatinine	Х				Х	Х	Х	
Urine pregnancy screen 	Х							
Research blood specimen 		Х	Х	Х	Х	Х	Х	
Anti-factor Xa level 			Х	+/- X				
SAE Monitoring			Х	Х	Х	Х	Х	Х
Bleeding event (based on focused interim H&P)			Х	Х	Х	Х	Х	Х
VTE event (based on focused interim H&P, with radiological confirmation when suspected clinically)			х	х	х	х	х	х
Telephone visit 								Х

Obtained for research purposes if not already being obtained clinically.

 For participants <20kg: (1) 3ml blue top tube and (1) 4mL CPT Tube (7mL total). For participants  $\ge$ 20kg, (1) 3mL blue top tube and (2) 4mL CPT tubes (11mL total). Research blood collection is for central research lab testing of D-dimer, Clot Formation and Lysis (CloFAL) assay, IL-6, and anti-SARS-CoV-2 IgG, as well as banking plasma, DNA isolated from the buffy coat, and peripheral blood mononuclear cells (PBMCs) for future research.

 Obtained at 4 hours after 1st or 2nd dose of enoxaparin, at initial dosage (mg/kg) and any subsequent change in dosage.

Focused, scripted assessment of symptoms of potential concern for bleeding events, VTE events, and SAEs. Refer to Manual of Operations.

\* If still hospitalized.

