#### Day 2 after enrollment (as inpatient)

- Interval focused interim history and physical with assessment for serious adverse events, bleeding event, and/or VTE event by inpatient medical provider
- Anti-factor Xa level (if enoxaparin dose sub- or supratherapeutic)
- Research blood specimen

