4.3. ANALYSIS OF THE SECONDARY OUTCOME

The secondary endpoint, twice-daily enoxaparin dose required to achieve target anti-Xa levels, will be summarized with medians and IQRs for all the study participants combined and by age group and MISC status. Distributions will be compared across groups, if there are adequate numbers in the groups, using Mann-Whitney U test.

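### Aim 2's recorded-dose median stays at 0.5 mg/kg over a roughly 2.5-fold range of true requirement, and ties weaken the age comparison for moderate differences

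*SAP*

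**What the plan says.** **Endpoint.** SAP 3.2 and Protocol IV.B define the secondary outcome as "Median twice-daily enoxaparin dose, as measured in mg/kg, required to achieve a 4 hour post-dose anti-factor Xa level of 0.20-0.49 anti-Xa U/mL". Hypothesis 2 (Protocol I.B) is that median requirements "are associated with age, with younger age groups requiring higher doses".

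**Dosing.** Protocol IV.D gives one starting rule for all ages: "Enoxaparin starting dose 0.5 mg/kg (max starting dose: 60 mg) subcutaneously q12 hours". The dose then moves in only two situations, with steps in per cent: "For anti-Xa values <0.20 U/mL, the enoxaparin dose will be increased by 10-20", and "For anti-Xa values ≥0.5 U/mL, the enoxaparin dose will be decreased by 10-20".

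**Levels.** Footnote 3 of Table 1 has levels taken "at initial dosage (mg/kg) and any subsequent change in dosage", 4 hours after the 1st or 2nd dose. The Day 2 list makes the repeat conditional: "Anti-factor Xa level (if enoxaparin dose sub- or supratherapeutic".

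**Analysis.** SAP 4.3 says the "twice-daily enoxaparin dose required to achieve target anti-Xa levels, will be summarized with medians and IQRs", overall and by age group and MIS-C status. Distributions are compared by Mann-Whitney if group sizes allow. Protocol IV.H plans Kruskal-Wallis with Bonferroni-adjusted pairwise tests. The aims name four age groups. SAP 4.1.2 splits at 12 years for the baseline table, and SAP 4.3 does not say which grouping it uses.

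**Not stated.** The documents give no rule for which dose counts as the one required (first in range, last, or lowest). They set no point target inside the band, make no use of the level itself in the Aim 2 analysis, and give no power or effect size for Aim 2.

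**The concern.** A child at 0.21 U/mL and a child at 0.48 U/mL on 0.5 mg/kg both stay on that dose, so both would be recorded as requiring 0.5 mg/kg. Their exposure per mg/kg differs by 0.48/0.21 = 2.3-fold. The endpoint can then report the dose everyone was started on rather than something learned about requirement. Age differences that play out inside the band become ties at 0.5, which weakens the test of Hypothesis 2 in a trial of 38 children. The levels that carry the missing information are collected but not used.

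**Working it through.** The plan states no figure for Aim 2, so there is none to reproduce.

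**Inputs from the documents.** Starting dose 0.5 mg/kg; band 0.20-0.49; action limits <0.20 and ≥0.5; steps of 10-20%; 38 children. The 60 mg cap binds only above 60/0.5 = 120 kg, so it is a minor exception.

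**Assumptions, not in the documents.** Level proportional to dose; lognormal variation between children, CV 40% unless stated; 15% steps; two-sided 5% tests; every child titrated until in range; the starting dose recorded for a child in range at the first level.

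**1. When the median is fixed.** The recorded median is 0.5 if fewer than half the children are below 0.20 and fewer than half are at 0.5 or above. For a population, this means the median level L on 0.5 mg/kg lies from 0.20 to below 0.50, a ratio of 0.50/0.20 = 2.5.

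**2. In terms of requirement.** For a reference level T, requirement R = 0.5 × T/L. Take T as mid-band, (0.20 + 0.49)/2 = 0.345:
- L = 0.20 gives R = 0.5 × 0.345/0.20 = 0.86 mg/kg.
- L = 0.50 gives R = 0.5 × 0.345/0.50 = 0.35 mg/kg.

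With T = 0.30 the window is 0.30 to 0.75.

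**3. Example.** At CV 40%, σ = √ln(1 + 0.4²) = 0.385.
- Median level 0.22: P(<0.20) = Φ(ln(0.20/0.22)/0.385) = 0.40.
- Median level 0.45: P(≥0.50) = 1 − Φ(ln(0.50/0.45)/0.385) = 0.39.

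Both are under one half, so both medians are 0.5, although requirement differs by 0.45/0.22 = 2.05-fold.

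**4. Outside the window.** For R = 1.0, L = 0.5 × 0.345/1.0 = 0.1725. One step gives 0.575 mg/kg and a level of 0.198, still low. Two steps give 0.661 mg/kg and 0.228, and titration stops near the lower edge. Simulated recorded medians are about 0.62 for a true 1.0 and 0.74 for a true 1.2.

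**5. In samples of 38** (CV 30-50%, 10% within-child noise):

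| True mid-band requirement, mg/kg | P(recorded median exactly 0.5) |
|---|---|
| 0.40 | 0.90-0.99 |
| 0.50-0.70 | ≥0.98 |
| 0.80 | 0.74-0.85 |
| 0.90 | 0.22-0.28 |
| 1.0 | ≤0.05 |
| 1.2 | about 0 |

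At a true 0.5-0.6, 66-87% of children are in range at the first level, and the IQR also collapses to 0.5-0.5.

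**6. Power, CV 40%, no assay noise.** Ranges cover different group sizes.

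| Median levels on 0.5 mg/kg, youngest first | Test | Recorded dose | Level per mg/kg |
|---|---|---|---|
| 0.20/0.26/0.32/0.36 | Kruskal-Wallis | 58-60% | 71-77% |
| 0.24/0.30/0.36/0.42 | Kruskal-Wallis | 47-54% | 66-72% |
| 0.17/0.24/0.28/0.32 | Kruskal-Wallis | 69-73% | 74-82% |
| 0.25 vs 0.35 | Mann-Whitney | 41-56% | 58-72% |
| 0.22 vs 0.45 | Mann-Whitney | 94-99% | not needed |

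The loss is about 5 (74 − 69) to 19 (66 − 47) points in the four-group scenarios and about 15-17 points for 0.25 vs 0.35. In the four-group trials the overall median was exactly 0.50 in 99-100%, with 63-70% of children tied there.

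**7. Sensitivity to CV and noise.** Two groups of 19, Mann-Whitney, 10% within-child noise. Entries are power on recorded dose, then on level per mg/kg:

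| True requirement, mg/kg | CV 30% | CV 40% |
|---|---|---|
| 0.60 vs 0.50 | 20%, 40% | 19%, 25% |
| 0.65 vs 0.50 | 40%, 68% | 36%, 47% |
| 0.70 vs 0.50 | 62%, 88% | 53%, 69% |
| 0.80 vs 0.50 | 91%, 99% | 85%, 93% |
| 1.0 vs 0.50 | 100%, 100% | 99%, 100% |

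In the first four rows both recorded group medians were 0.5.

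**The case against.** The strongest reply is that the endpoint is defined against a range. For a child in range on 0.5 mg/kg, that dose does achieve the stated target, and the dose for one fixed level is a question the Protocol never asks. This stands in part: 0.5 is a correct answer for such a child, but so are many other doses, because the documents neither say which one counts nor set a point inside the band.

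Second, a reader might infer that the plan cannot tell apart populations whose requirement differs two-fold. The documents do not support that. SAP 4.3 reports IQRs and compares distributions, not medians alone. A rank test uses the shares titrated up or down, so it separates 0.22 from 0.45 with 94-99% power while both medians sit at 0.5.

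Third, the CV, age gradients and group sizes are assumed, and the four-group figures use the Protocol's test rather than the SAP's. This is fair. Both tests are therefore shown, and the loss is conditional.

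Fourth, level per mg/kg has its own weaknesses. It depends on whether sampling followed the 1st or 2nd dose and on prior prophylactic enoxaparin, which the exclusion criteria permit. Repeat levels exist only for children first found out of range. Replacing the planned test would also be hard to defend in an open-label trial whose SAP (2.5) already reports 38 enrolled. These points stand; they argue for an added analysis, not a replacement.

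**Conclusion.** The point holds within limits. If the starting dose is what gets recorded for children in range at once, the Aim 2 median is 0.5 mg/kg over a roughly 2.5-fold range of true requirement (about 0.35-0.86 mg/kg for a mid-band reference). A reader might infer that 0.5 comes back almost whatever the truth. It does not: at a true 1.0 or more the sample median is rarely or never 0.5, though it is biased toward it.

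For the age comparison, ties matter for moderate effects: about 5-19 points of power at an assumed CV of 40%, and up to 28 points (68 − 40) in the CV 30% runs. At a two-fold difference in requirement the loss is 0-1 point. All power figures rest on assumed variability and gradients and on proportionality of level to dose. Aim 2 is secondary and its comparison is conditional on adequate numbers, so this is an inexpensive improvement to the analysis and does not invalidate the plan.

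**What to change.** In SAP 4.3:

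1. Keep the planned recorded-dose median, IQR and test.
2. State which dose is recorded as the one required.
3. Report the percentage of children in range at the starting dose, overall and by age group, so that a median of 0.5 can be read correctly.
4. Add a supportive analysis of Hypothesis 2 on the 4-hour level per mg/kg, or a mixed model of log anti-Xa on log dose and age using every level, with 90% CIs by age group. Specify it before the SAP is finalised, and label it as added after enrolment.
5. Record, or adjust for, sampling after the 1st or 2nd dose and prior prophylactic enoxaparin.

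The cost is SAP wording and a few lines of code; the levels and doses are already collected. The added analysis assumes rough proportionality, which can be checked only in the selected children with repeat levels, so it should be reported beside the planned result and not in its place. No dose or titration rule changes.

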3.3. EXPLORATORY OUTCOMES

Proportion of plasma D-dimer levels <2x ULN; cumulative incidence of VTE; and duration of assisted ventilation (Mechanical ventilation, Non-invasive ventilation and Extracorporeal life support).

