#### F. Description and Justification of Procedures, Measures, and Data Collection Tools:

There will be minimal laboratory assays, examinations, or other procedures performed solely for the purposes of this study and not currently part of best/standard clinical care.

The first is an additional 11 mL blood specimen (7mL in participants <20kg) obtained at visits on post-enrollment days 1 and 2 (and days 3, 7, and 14 if still hospitalized) for protocol-specified research laboratory investigations (D-dimer, IL-6, anti-SARS-CoV-2 IgG/IgM, and CloFAL assay) and future unspecified research (i.e., banking of plasma, DNA isolated from the buffy coat, and isolated PBMCs). These biospecimens will be stored in the Johns Hopkins All Children's Pediatric Biorepository at the Clinical Coordinating Center. All biospecimen storage tubes are pre-labeled with a unique 2D

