#### Screening/Within 72 hours of hospital admission (Day 0)

- Informed consent
- Enrollment
- Full medical history and physical exam
- Weight
- Initial plasma laboratory evaluation including the following (obtained as research purposes if not already obtained clinically
  - Complete blood cell count with platelet count
  - o PT and aPTT
  - o Fibrinogen
  - Serum creatinine
  - Urine pregnancy screening (beta-HCG)
- Research blood specimen collection

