# H. Data Analysis Plan:

The statistical analysis plan was developed by the lead trial biostatistician. Subject demographics and characteristics at study entry will be summarized with counts and percentages for categorical variables, and with means, standard deviations, medians, and interquartile ranges (IQR) as appropriate, for numeric variables. Missing data will not be imputed. Analysis of the primary endpoint will be conducted on the safety population, which includes all subjects who receive at least one dose of enoxaparin. The primary endpoint, cumulative incidence of ISTH-defined [11] clinically-relevant bleeding events during hospitalization, will be calculated with the corresponding exact (Clopper-Pearson) 90% confidence intervals (90%CIs). The precision of estimates for different cumulative incidences of clinically-relevant bleeds and corresponding 90% Cis are as follows: 0/38, 0% (0-7.6)%; 1/38, 2.6% (0-11.8%); 2/38, 5.3% (0-15.7%). The secondary endpoint, twice-daily enoxaparin dose required to achieve target anti-Xa levels, will be summarized

with medians and IQRs for all the study participants combined and by age group. Medians will be compared across age groups, if there are adequate numbers in the groups, using the Kruskal-Wallis test and a *post-hoc* Bonferroni-adjusted Mann-Whitney U test, if needed. The tertiary endpoints (as outlined in Section IV.B) will be calculated as proportions and cumulative incidences with 90%CIs, and medians with IQRs.

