4.4. ANALYSIS OF THE TERTIARY OUTCOMES

The tertiary outcomes will be calculated as proportions and cumulative incidences with 90%CIs, and medians with IQRs for all the study participants combined and by age group and MISC status

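### The D-dimer measure counts repeated levels rather than children, and SAP 4.4 gives it a 90% CI without a method that allows for clustering or for more samples from long-stay children

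*SAP*

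**What the plan says.** SAP 1.3 (Aim 3a) measures surrogate efficacy by the "proportion of serial D-dimer levels obtained at standardized time points" that fall below twice the age-specific upper limit of normal. SAP 3.3 shortens this to "Proportion of plasma D-dimer levels <2x ULN". In both places the thing counted is a level, and the word serial means several per child.

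For the analysis, SAP 4.4 says: "The tertiary outcomes will be calculated as proportions and cumulative incidences with 90%CIs". Protocol section H has the equivalent line: "will be calculated as proportions and cumulative incidences with 90%CIs, and medians with IQRs". Neither document names a per-child summary, an analysis by day, a clustered variance or a weighting rule for this outcome. Clopper-Pearson is named only for the primary bleeding endpoint (protocol H, SAP 4.2). SAP 4.1.4 specifies complete cases without imputation and does not address unequal numbers of samples per child.

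The levels come from the research blood specimen. The opening text of protocol section F says it is "obtained at visits on post-enrollment days 1 and 2 (and days 3, 7, and 14 if still hospitalized". Table 1 also marks a specimen at Day 0, and the Day 0 visit list in section F includes "Research blood specimen collection".

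**The concern.** Two features of the sampling matter once levels are counted instead of children.

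- **Correlation.** Successive D-dimer values in one acutely ill child are unlikely to be independent. A binomial interval treats each level as a new piece of information, so it claims more precision than 38 children can give.
- **Unequal numbers.** Everyone is scheduled for days 1 and 2, but days 3, 7 and 14 depend on still being in hospital. Longer stays earn more weight. If stay is related to D-dimer, the pooled proportion moves with discharge patterns. SAP 4.4 also reports by age group and MIS-C status, where numbers are smaller and stays may differ, so an apparent subgroup difference could partly reflect sample counts.

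The role of Day 0 is also undefined. SAP 3.3.1 lists D-dimer among the demographic and clinical characteristics, so the same value could serve as a baseline descriptor and as an efficacy observation.

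At stake is whether the reported 90% interval has roughly 90% coverage, and whether the point estimate describes children or samples.

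**Working it through.** The documents give no numerical figure for the D-dimer measure, so there is nothing of the plan's own to reproduce.

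**Inputs from the documents**
- 38 children (SAP 4.5); 90% confidence level (SAP 4.4).
- Post-enrollment levels per child: 2 (days 1 and 2) to 5 (adding days 3, 7 and 14). With Day 0: 3 to 6.

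**Assumed, because the documents do not say**
- Within-child correlation (ICC) 0.3 to 0.7, with 0.1 as a low case.
- True proportion 0.3 to 0.5.
- Distribution of stay. For the hand calculation: 8, 15, 12 and 3 children with 2, 3, 4 and 5 post-enrollment levels.

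**Step 1: design effect, Day 0 excluded**
- Total levels: 8×2 + 15×3 + 12×4 + 3×5 = 124.
- Sum of squares: 8×4 + 15×9 + 12×16 + 3×25 = 434.
- Weighted cluster size: 434/124 = 3.5.
- Design effect DE = 1 + (3.5 − 1)×ICC. Effective n = 124/DE.
- Half-width at p = 0.5: 1.645×√(0.25/124) = 7.4 points if pooled, multiplied by √DE if clustered.
- Approximate coverage of the pooled interval: 2Φ(1.645/√DE) − 1.

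| ICC | DE | Effective n | Clustered half-width (points) | Coverage of pooled interval |
|---|---|---|---|---|
| 0 | 1.00 | 124 | 7.4 | 90% |
| 0.3 | 1.75 | 71 | 9.8 | 79% |
| 0.5 | 2.25 | 55 | 11.1 | 73% |
| 0.7 | 2.75 | 45 | 12.2 | 68% |

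**Step 2: simulation.** Beta-binomial levels for 38 children, log-normal stay with an assumed median of 5 days, days 1 and 2 for all and days 3, 7 and 14 if still in hospital (about 120 levels), with a pooled Clopper-Pearson 90% interval. Coverage was about 68-82% for ICC 0.3 to 0.7 and about 88% at ICC 0.1. At p = 0.5 the true standard error was about 0.06-0.07, against a binomial 0.045.

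**Step 3: if Day 0 is pooled as well.** An assumed mix of 8, 15, 12 and 3 children with 3, 4, 5 and 6 levels gives 24 + 60 + 60 + 18 = 162 levels. At p = 0.5, simulated coverage of the pooled interval was 74%, 68% and 63% for ICC 0.3, 0.5 and 0.7. An interval clustered on the child gave 89-90%.

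**Step 4: weighting.** A child with all post-enrollment samples counts 5/2 = 2.5 times one with only days 1 and 2 (6/3 = 2 times with Day 0). As an illustration, let half the children be long-stay with 20% of levels below the threshold and half short-stay with 60%. The child average is 40%. The pooled figure is (5×0.20 + 2×0.60)/7 = 31% without Day 0, or (6×0.20 + 3×0.60)/9 = 33% with it. In the simulation, a correlation of 0.5 between high D-dimer and longer stay moved the pooled mean to 45-47% against a child average of 50%. With no such link there is no drift.

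**Step 5: Day 0.** Table 1 and the Day 0 visit list in section F both include the specimen. Only the opening text of section F leaves it out. Neither document says whether that value enters the proportion.

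**The case against.** The strongest reply is that neither document says that levels will be pooled across days or given a binomial interval. SAP 4.4 is one summary line covering three outcomes, and the reference in Aim 3a to "as measured by the proportion of serial D-dimer levels obtained at standardized time points" would fit a proportion per day, with one level per child and no clustering. That stands in part: the narrow interval is what the plain text leads to, not something the SAP commits to. However, a single proportion of levels does not describe a by-day analysis, and no text points to a clustered method. Even by day, days 3, 7 and 14 would describe only children still in hospital.

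It is also fair that a proportion of levels is a legitimate descriptive quantity, that the ICC and the link with stay are assumed, and that at an ICC of 0.1 the loss of coverage is small. The outcome is exploratory, has no hypothesis or threshold, and does not enter the sample size or the pause rules in Table 2.

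Three stronger readings are not supported:
- A reader might infer that the estimate is biased downward. The direction and size depend on how D-dimer relates to stay, which the documents do not give.
- A reader might infer that section F as a whole contradicts Table 1 on Day 0. The visit list within section F agrees with Table 1.
- A reader might treat Day 0 as an untreated baseline. The exclusion criteria in both documents allow prophylactic enoxaparin before enrollment.

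**Conclusion.** The concern holds as a gap in specification with a predictable consequence. If the text is followed plainly, a nominal 90% interval covers about 68-82% for an ICC of 0.3 to 0.7, with about 120 post-enrollment levels and a true proportion of 0.3 to 0.5, and about 88% at an ICC of 0.1. The direction holds for any positive within-child correlation; the size is assumption-dependent. The shift in the point estimate is conditional: about 3 to 5 points at an assumed correlation of 0.5 between high D-dimer and longer stay, and none without such a link.

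A reader might go further and infer that the flaw distorts an estimate of drug effect. This is a single-arm trial, so no version of the measure isolates one. The primary safety conclusion is unaffected. It is a cheap improvement to an exploratory outcome.

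**What to change.** In SAP 4.4:
- Report the proportion of children below twice the upper limit of normal at each scheduled post-enrollment day, with the number sampled and an exact 90% CI. State that days 3, 7 and 14 describe only children still in hospital.
- If one overall figure is wanted, use the mean of per-child proportions with a 90% CI from a bootstrap that resamples children. A GEE with independence working correlation is not enough: it widens the interval but returns the pooled estimate, so the extra weight on long-stay children remains.
- Summarise Day 0 separately as the enrollment value, noting that some children may already have received prophylactic enoxaparin, and keep it out of the efficacy proportion.

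In the protocol, align the opening text of section F with Table 1 and the Day 0 visit list on whether a Day 0 specimen is taken.

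The cost is a few sentences and a few lines of code, with no new data. The overall interval becomes wider: in the 124-level example at p = 0.5, the design-effect half-width is roughly 10 to 12 points instead of 7.4.
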